6.1.1 Sample size calculations for safety

The goal of the safety evaluation for this study is to identify safety concerns associated with product administration. The ability of the study to identify SAEs can be expressed by the true event rate above which at least 1 event would likely be observed and the true event rate below which no events would likely be observed. Specifically, in the Group 1 vaccine arm ($n = 5$), there is at least a 90% chance of observing at least one event, if the true rate is 37% or more, and there is at least a 90% chance of observing no events, if the true rate is 1% or less. In the Group 2 vaccine arm ($n = 15$), there is at least a 90% chance of observing at least 1 event if the true rate of such an event is 14.3% or more, and there is at least a 90% chance of observing no events if the true rate is 0.6% or less. In all vaccine arms of the study combined ($n = 20$), there is at least a 90% chance of observing at least one event, if the true rate is 10.9% or more, and there is at least a 90% chance of observing no events, if the true rate is 0.5% or less.

As a reference, in HVTN vaccine trials from April 2008 through March 2018 conducted in the US, about 1.7% of participants who received placebos experienced an SAE.

Binomial probabilities of observing 0, 1 or more, and 2 or more events among arms of size 15 and 5 are presented in Table 6-1 for a range of possible true adverse event rates. These calculations provide a more complete picture of the sensitivity of this study design to identify potential safety problems with the vaccine.

Table 6-1 Probability of observing 0 events, 1 or more events, and 2 or more events, among arms of size 15 and 5, for different true event rates

True event rate (%)	Pr(0/15)	Pr(1+/15)	Pr(2+/15)	Pr(0/5)	Pr(1+/5)	Pr(2+/5)
1	86	14	1	95.1	4.9	0.1
5	46.3	53.7	17.1	77.4	22.6	2.3
10	20.6	79.4	45.1	59	41	8.1
20	3.5	96.5	83.3	32.8	67.2	26.3
30	0.5	99.5	96.5	16.8	83.2	47.2
40	0	100	99.5	7.8	92.2	66.3

An alternative way of describing the statistical properties of the study design is in terms of the 95% confidence interval for the true rate of an adverse event based on the observed data. [Table 6-2](#) shows the 2-sided 95% confidence intervals for the probability of an event based on a particular observed rate. Calculations are done using the score test method (33). If none of the 20 participants receiving a vaccine regimen experience a safety event, the 95% 2-sided upper confidence bound for the true rate of such events in the total vaccinated population is 16%. For the Group 1 vaccine arm (n = 5), the 2-sided upper confidence bound for this rate is 43%. For the Group 2 vaccine arm (n = 15), the 2-sided upper confidence bound for this rate is 20%.

Table 6-2 Two-sided 95% confidence intervals for the probability of observing a safety event based on observing a particular rate of safety endpoints for arms of size 5, 15 and 20

Observed event rate	95% Confidence interval (%)
0/5	[0, 43.4]
1/5	[3.6, 62.4]
2/5	[11.8, 76.9]
0/15	[0, 20.4]
1/15	[1.2, 29.8]
2/15	[3.7, 37.9]
0/20	[0, 16.1]
1/20	[0.9, 23.6]
2/20	[2.8, 30.1]

6.1.2 Sample size calculations for immunogenicity

The main goals of this trial regarding immunogenicity outcomes involve a preliminary estimation of rates of “response” (defined as binding response positivity to the 2F5 epitope) based on data from immune assays among vaccinees. To address binding antibody endpoints, the analysis will descriptively summarize binding response positivity call rates, and for the comparison of Group 1 vs 2, test superiority of the rate of responses targeting the 2F5 binding site by Barnard’s exact test. No adjustment for multiple comparisons will be made for the use of multiple assays. The precision with which the true response rate can be estimated from the observed data depends on the true underlying response rate

and the sample size. Two-sided 95% confidence intervals for the response rate based on observing a particular rate of responses in the vaccinees is shown in [Table 6-3](#). Calculations are done using the score test method (33). The $n = 4$, $n = 13$, and $n = 18$ (for the two arms combined) assume a 10% rate of missing immunogenicity data.

Table 6-3 Two-sided 95% confidence intervals for the true response rate based on observing a particular rate of responses in the vaccinees ($n = 4$, $n = 13$, and $n = 18$)

No. of responses	Observed response rate (%)	95% Confidence interval
1/4	25	[4.6, 69.9]
2/4	50	[15, 85]
3/4	75	[30.1, 95.4]
1/13	7.7	[1.4, 33.3]
3/13	23.1	[8.2, 50.3]
5/13	38.5	[17.7, 64.5]
7/13	53.8	[29.1, 76.8]
9/13	69.2	[42.4, 87.3]
3/18	17	[5.8, 39.2]
6/18	33	[16.3, 56.3]
9/18	50	[29, 71]
12/18	67	[43.7, 83.7]
15/18	83	[60.8, 94.2]

An alternative approach is to consider the probability of observing 0, 1 or more, and 50% or more responses for groups of sizes 4, 13 and 18; presented in [Table 6-4](#) for a range of possible true response rates. If the true rate is 20%, then there is a 59% chance of observing any responses in the Group 1 vaccine arm, a 94.5% chance of observing any responses in the Group 2 vaccine arm and a 98% chance of observing at least one response across the two arms. In all cases, the probability of observing 50% or more positive responses is in excess of 80% if the true positivity rate is at least 60%, but when the true rate is below 40%, there is at least a 50% chance of observing fewer than half respond. If the true rate is 50%, then there is a 59% chance of observing at least half (2) respond in the $n = 4$ Group 1 vaccine arm, a 71% chance of observing at least half (6, rounding down) respond in the $n = 13$ Group 2 vaccine arm and a 59% chance of observing at least half (9) respond across the two arms combined ($n = 18$).

Table 6-4 Probability of observing 0 events, 1 or more events, and 50% or more events, among groups of size 4, 13 and 18, for different true event rates

True rate (%)	Pr(0/4)	Pr(1+/4)	Pr(2+/4)	Pr(0/13)	Pr(1+/13)	Pr(6+/13)	Pr(0/18)	Pr(1+/18)	Pr(9+/18)
10	65.6	34.4	5.2	25.4	74.6	0.1	15	85	0
20	41	59	18.1	5.5	94.5	3	1.8	98.2	0.4
30	24	76	34.8	1	99	16.5	0.2	99.8	6
40	13	87	52.5	0.1	99.9	42.6	0	100	26.3
50	6.2	93.8	68.8	0	100	70.9	0	100	59.3
60	2.6	97.4	82.1	0	100	90.2	0	100	86.5
70	0.8	99.2	91.6	0	100	98.2	0	100	97.9
80	0.2	99.8	97.3	0	100	99.9	0	100	99.9
90	0	100	99.6	0	100	100	0	100	100

As shown in [Table 6-5](#), there is limited power for a formal comparison of immunogenicity response rates between vaccine arms of size $n = 13$ vs $n = 4$. For either 80% or 90% power, the sizes of differences that the trial is powered to detect are fairly large. These calculations use a Fisher's exact 2-sided test with a Type I error rate of 0.05.

Table 6-5 Power for comparison of response rates between 2 arms ($n_1 = 13$, $n_2 = 4$)

True response rate Arm 1 (%)	Minimum true response rate in Arm 2 in order to detect a difference	
	80% power	90% power
0	89	97
1	90	97
2	91	98
3	92	99
4	92	99
5	93	100

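### Section 6.1.2 gives Group 1 a 59% chance of at least 2 of 4 responding at a 50% true rate, but the exact value and Table 6-4 are 68.8%; the Group 2 figure for at least half counts 6 of 13 (46%)

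*Combined protocol and SAP*

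**What the plan says.** Section 6.1.2 describes precision and operating characteristics for the immunogenicity response rate, using 4, 13 and 18 evaluable vaccinees (Group 1, Group 2 and both combined) after allowing for 10% missing data. The title of Table 6-4 describes it as "Probability of observing 0 events, 1 or more events, and 50% or more events, among groups of size 4, 13 and 18".

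The text above the table evaluates a 50% true rate. For Group 1, "then there is a 59% chance of observing at least half (2) respond in the" arm of 4. For Group 2 it gives "a 71% chance of observing at least half (6, rounding down) respond in the" arm of 13. For the two arms combined it gives 59% for 9 or more of 18.

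In the 50% row, Table 6-4 prints Pr(2+/4) = 68.8, Pr(6+/13) = 70.9 and Pr(9+/18) = 59.3. The text also makes a general claim for all three sizes: "the probability of observing 50% or more positive responses is in excess of 80% if the true positivity rate is at least 60" per cent.

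**The concern.** There are two separate problems.

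The first is numerical. The text and the table give different probabilities (59% and 68.8%) for the same event, sample size and true rate, so one must be wrong.

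The second concerns the event. With 13 participants exactly half cannot occur, and the smallest count that is at least half is 7. Rounding down to 6 admits a result of 46.2%, below the stated minimum. The table title and the general 80% claim nevertheless describe the Group 2 event as 50% or more. The rounding affects only the arm of 13, because half of 4 and half of 18 are whole numbers, so the three figures set side by side do not share one definition.

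At stake is the accuracy of the sample size section. Its immunogenicity aim is preliminary estimation of response rates, and Section 6.1.2 itself says that power for a formal comparison between arms is limited. These descriptive probabilities therefore carry a fair share of the justification.

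**Working it through.** **Inputs.** Evaluable sizes 4, 13 and 18 (Section 6.1.2, with Tables 6-3 and 6-4); a true rate p of 50% and the cut-offs 2, 6 and 9 (text of Section 6.1.2); p of 40%, 60% and 70% (rows of Table 6-4).

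**Formula.** The number of responders X is binomial (n, p), and P(X ≥ r) = Σ C(n,k) p^k (1−p)^(n−k) over k = r, …, n.

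**1. The plan's three figures at p = 0.5.**

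- Group 1: P(X ≥ 2 | n = 4) = 1 − (1 + 4)/16 = 11/16 = 68.75%. The text says 59%; Table 6-4 says 68.8%. The text is low by 68.75 − 59 = 9.75 points.
- Group 2: P(X ≥ 6 | n = 13) = 70.95%. The text says 71% and the table 70.9%. Both agree for this cut-off.
- Combined: P(X ≥ 9 | n = 18) = 59.27%. The text says 59% and the table 59.3%. Both agree.

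Only the Group 1 figure fails to reproduce. Other readings at p = 0.5 do not rescue it: 1+/4 gives 93.8%, 3+/4 gives 31.3%, 2+/5 gives 81.3% and 3+/5 gives 50.0%. The number 59 does appear nearby, for 9+/18 at 50% (59.3%) and for 1+/4 at 20% (59.0%). A copying slip is plausible, but the documents do not show the cause.

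**2. The Group 2 cut-off.** 6/13 = 46.2% and 7/13 = 53.8% (Table 6-3 prints the latter). The two events differ by P(X = 6):

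| True rate | 6+/13 (printed) | 7+/13 (at least half) | Difference, points |
|---|---|---|---|
| 40% | 42.6% | 22.9% | 19.7 |
| 50% | 70.9% | 50.0% | 20.9 |
| 60% | 90.2% | 77.1% | 13.1 |
| 70% | 98.2% | 93.8% | 4.4 |

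At 50% the 7+/13 value is exactly one half by symmetry: with 13 participants, either 7 or more respond or 7 or more do not.

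**3. The three sizes under one definition.** At a 50% true rate, the chance that at least half respond is 68.8% (n = 4), 50.0% (n = 13) and 59.3% (n = 18). The text gives 59%, 71% and 59%. Group 2 moves from the highest of the three to the lowest.

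**4. The 80% claim at a 60% true rate.** P(2+/4) = 1 − 0.4⁴ − 4 × 0.6 × 0.4³ = 1 − 0.0256 − 0.1536 = 82.1%. P(9+/18) = 86.5%. For Group 2, P(6+/13) = 90.2% but P(7+/13) = 77.1%, and the latter reaches 80% only at a true rate of about 61.3%. The claim holds as computed but not as worded.

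**5. A minor companion sentence.** The text says that below a 40% true rate there is at least a 50% chance that fewer than half respond. For n = 4, P(2+/4) crosses 50% at a true rate of 38.6%. At 39%, the chance of fewer than 2 of 4 is 0.61⁴ + 4 × 0.39 × 0.61³ = 0.1385 + 0.3541 = 49.3%, so the sentence fails narrowly between about 38.6% and 40%.

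**The case against.** The strongest reply is that the Group 2 cut-off is not hidden. The text says it rounds down to 6, the column is headed with 6+, and every value in that column is right for that event. On this view the matter is one of labelling and not arithmetic, and the 80% claim is simply a reading of the 60% row of Table 6-4, where the three entries (82.1, 90.2 and 86.5) all exceed 80%. All three figures also assume the same true rate, so differences between them reflect sample size and cut-off and say nothing about which dose is better. Nothing in the plan uses at least half as a criterion: dose escalation rests on safety data. The sentence about rates below 40% fails only by a fraction of a point to a few points, on a table built in steps of 10.

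Most of this stands. The Group 2 point is a labelling error, the reordering concerns operating characteristics and not doses, and the 40% item is marginal. Two things remain. The objection offers no defence of the 59%, which the adjacent table contradicts. And stating the rounding once does not make the table title or the general 80% claim true, since both still name an event of 50% or more and carry no caveat.

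**Conclusion.** The concern holds. The Group 1 figure in the text is wrong: 59% should be 68.75%, as Table 6-4 already shows. The Group 2 figures are correct for 6 or more of 13 but do not describe at least half. For that event they are overstated by about 20, 21, 13 and 4 points at true rates of 40%, 50%, 60% and 70%, and the 80% claim is not met between 60% and about 61.3%.

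This rests only on the plan's own evaluable sizes and on independent responses with a common true rate, the model that reproduces the other figures in the same sentence. The effect is confined to descriptive text. The Table 6-4 entries match their column headings, the probabilities of no response and of at least one response are right, and no sample size, test or decision rule changes. It should be corrected because it is a definite error in stated operating characteristics and is cheap to repair.

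**What to change.** - In the text of Section 6.1.2, change the Group 1 probability at a 50% true rate from 59% to 69%.
- For Group 2, choose one of two courses:
  - Keep the numbers, and describe the event as 6 or more of 13 (46%) everywhere, including the Table 6-4 title and the 80% claim; or
  - Replace the Pr(6+/13) column with Pr(7+/13), which at true rates of 10% to 90% in steps of 10 is 0.0, 0.7, 6.2, 22.9, 50.0, 77.1, 93.8, 99.3 and 100.0%; change 71% to 50%; and restate the 80% claim to say that Group 2 has 77% at a 60% true rate.
- Optionally, change the limit in the companion sentence from below 40% to at or below 38%.

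The cost is text edits, plus one table column under the second course. The Group 1 figure rises by about 10 points. The Group 2 figures fall only if 7 or more of 13 is adopted; relabelling leaves them unchanged.

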4.7.1.4 NHP Study #204 and #205

Two NHP studies were designed to evaluate the effects of the adjuvant regimens (GLA or alum) on the immunogenicity of the MPER-656 liposome product. NHP 204 tested the immunogenicity of the MPER-656 liposome product formulated with GLA or GLA plus alum (n=8 per group), and NHP 205 tested the MPER-656 liposome vaccine with alum alone (n=7), as described by Bradley et al. (18). Rhesus macaques were immunized with 1 mg of MPER-656 liposomes six times,

six weeks apart, formulated with either 25 mcg of GLA, or 500 mcg alum, or a combination of both adjuvants.

After 2 immunizations in rhesus macaques, MPER-656-specific antibodies were present in all animals in the alum alone and GLA plus alum arms but not in the GLA-alone adjuvant arm. Sequential vaccinations did not further boost the immune response above that observed following the 2nd injection, perhaps due to hyperimmunization at 6-week intervals (18), a period shorter than that proposed for the current study.

These NHP studies demonstrated that the MPER peptide contained within liposomes was antigenic and can be used to generate antibodies against the 2F5 epitope in immunized NHPs after >1 immunization. The data also support the use of alum as an adjuvant in this phase 1 clinical study. A neutralizing antibody response was not detected in these NHPs, likely due to the immune tolerance control mechanisms indicated above for NHP 22 study (Section 4.7.1.3), but data from that study did indicate that the vaccine regimen could begin the maturation process for 2F5-like antibodies, and this phase 1 study will determine whether the same initiation of bnAb lineages can occur in humans.

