4.7.1.5 NHP Study #208

A dose study was performed in Rhesus macaques (NHP 208) to test three vaccine doses of MPER-656 liposomes mixed with alum (Alhydrogel®). This study covered the dose range used for the preclinical GLP toxicity study and the proposed HVTN clinical study (0.2, 1.0, and 2.0 mg MPER-656 liposomes, all with 0.5 mg alum adjuvant). There were also 2 control groups—2.0 mg MPER liposomes without alum, and empty liposomes plus 0.5 mg alum (N=4/ group). All animals were immunized at weeks 0, 4, and 8 (three immunizations) and bled on the immunization days, two weeks after each immunization, and a final bleed was collected at 12 weeks (four weeks after the last immunization) for antibody binding titers. Plasma antibody binding results at the week 12 timepoint showed that adjuvant was required to achieve the highest MPER-binding titers in this study, but there was no significant difference in MPER antibody titers between the tested doses (Figure 4-2).

[figure not shown]

Figure 4-2 Alum adjuvant significantly enhances MPER-specific antibodies in rhesus macaques. At week 12, four weeks after the final immunization, MPER-binding plasma antibodies were detected by ELISA. Data are shown as the log-transformed area under the curve (AUC) values with each data point representing a single animal. Alum significantly enhanced antibodies levels at all MPER-peptide liposome doses, and there were no significant differences between the three doses ($P < 0.05$; Wilcoxon Mann-Whitney compared to no adjuvant).

There is only a 4-fold difference between the lowest and highest doses planned for the clinical trial. There was no significant difference in MPER-specific binding antibodies tested at week 12 between any of the treatment groups in this NHP study.

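### Table 6-5 shows power for the 500 vs 2000 mcg comparison only at comparator rates of 0–5%, and Section 6.1.2 does not say that 80% power is out of reach once the 500 mcg response rate exceeds about 42%

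*Combined protocol and SAP*

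**What the plan says.** Primary objective 2 (Section 5.1) concerns binding antibody responses at different doses of the vaccine. Section 6.1.2 makes preliminary estimation of response rates the main immunogenicity goal. For Group 1 (500 mcg) against Group 2 (2000 mcg) it also plans to "test superiority of the rate of responses targeting the 2F5 binding site by" Barnard's exact test. Section 6.4.4.1 sets significance at a two-sided p-value of 0.05 or less and generally prefers Barnard's test to Fisher's.

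The evaluable numbers, 4 and 13, "assume a 10% rate of missing immunogenicity data". Section 6.1.2 then says that "there is limited power for a formal comparison of immunogenicity response rates between vaccine arms of size" 13 and 4, and adds: "For either 80% or 90% power, the sizes of differences that the trial is powered to detect are fairly large". It describes the method as follows: "These calculations use a Fisher's exact 2-sided test with a Type I error rate of 0.05".

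Table 6-5 has six rows. The column headed "True response rate Arm 1" runs 0, 1, 2, 3, 4 and 5%. The minimum Arm 2 rates are 89, 90, 91, 92, 92 and 93% for 80% power, and 97, 97, 98, 99, 99 and 100% for 90% power. No reason is given for stopping at 5%. Table 6-4, in the same section, uses true rates of 10 to 90% for the same arms, so the two tables have no rate in common.

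**The concern.** Both arms in this comparison receive vaccine with alum. A range of 0 to 5% would suit a comparator expected to be almost entirely non-responding, and nothing in the documents supports that expectation for the 500 mcg dose. The animal data give no reason to confine the range there. After two 1 mg immunizations, "MPER-656-specific antibodies were present in all animals in the alum alone and GLA plus alum arms" (Section 4.7.1.4). In the macaque dose study of 0.2, 1.0 and 2.0 mg, "there was no significant difference in MPER antibody titers between the tested doses" (Section 4.7.1.5).

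The text tells the reader that power is limited but that a large enough difference can be detected with 80% or 90% power. With four evaluable participants in one arm, that stops being so at some comparator rate, because even a 100% response in the other arm cannot reach significance often enough. If the 500 mcg rate lies above that point, a non-significant result says almost nothing about a dose effect, and Section 6.1.2 does not warn of this.

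**Working it through.** **Inputs.** Group 1 n = 4 and Group 2 n = 13 (5 and 15 less 10%, rounded down; Section 6.1.2). Two-sided 0.05 (Sections 6.1.2 and 6.4.4.1). Power targets 80% and 90%. The human response rate at 500 mcg is not in the documents, so it is varied.

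**Step 1: reproduce the printed table.** All 12 cells follow from an arcsine normal approximation with continuity correction, taking Arm 1 as the n = 4 arm and Arm 2 as the n = 13 arm:

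power = Φ(h·√(4·13/17) − 1.96), with h = 2·asin√(p₂ − 1/26) − 2·asin√(p₁ + 1/8).

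For p₁ = 0 and p₂ = 0.89: h = 2·asin√0.8515 − 2·asin√0.125 = 1.628, and 1.628 × 1.749 − 1.96 = 0.887, so power is 81.2%. The minimum p₂ values before rounding up are 88.1, 89.1, 90.2, 91.1, 92.0 and 92.8 (80%) and 96.1, 96.9, 97.6, 98.2, 98.8 and 99.4 (90%). Rounded up, they equal the printed cells. Full enumeration of Fisher's test does not reproduce them. For the 0% row it gives 75.3/80.0, and pooled Barnard gives 68.5/73.7, against 89/97 printed. The caption's order (n1 = 13, n2 = 4) is the reverse of the column order that reproduces the cells.

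**Step 2: the best case for Group 2.** Suppose all 13 Group 2 participants respond.

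- Against 2/4 in Group 1, the two-sided Fisher p is C(4,2)/C(17,2) = 6/136 = 0.044: significant.
- Against 3/4, it is 4/17 = 0.235: not significant.
- Pooled Barnard gives 0.017 and 0.110, so the cut-off is the same.

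Maximum power to show Group 2 higher is therefore Pr(X ≤ 2), with X binomial (4, p) and p the Group 1 rate.

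| Group 1 rate | 30% | 40% | 50% | 60% | 70% | 80% | 90% |
|---|---|---|---|---|---|---|---|
| Maximum power | 91.6% | 82.1% | 68.8% | 52.5% | 34.8% | 18.1% | 5.2% |

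These are the plan's own Table 6-4 entries for 2 or more of 4, read at the complementary rate, since Pr(X ≤ 2 at p) = Pr(X ≥ 2 at 1 − p). The limit is p = 41.7% for 80% power (80.1% there, 79.9% at 41.8%) and 32.0% for 90% power.

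**Step 3: minimum Group 2 rates, pooled Barnard, full enumeration at 4 vs 13.**

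| Group 1 rate | 80% power | 90% power |
|---|---|---|
| 0% | 68.5 | 73.7 |
| 5% | 74.7 | 82.1 |
| 10% | 81.0 | 88.3 |
| 20% | 89.9 | 95.8 |
| 30% | 96.0 | 99.6 |
| 40% | 99.6 | not attainable |
| 50% or more | not attainable | not attainable |

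For a true 50% against 90%, power is 31% (Fisher) or 37% (pooled Barnard).

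**Step 4: how far the limit moves (80% power).**

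| Setting | Highest comparator rate |
|---|---|
| 4 vs 13, Fisher or pooled Barnard | 41.7% |
| 5 vs 15, Fisher | 32.6% |
| 5 vs 15, pooled Barnard | 50.9% |
| n = 13 arm as comparator, Fisher / Barnard | 24.7% / 31.5% |
| Approximation behind Table 6-5, n = 4 as comparator | 16.8% |
| 4 vs 13, Barnard with unpooled statistic | about 5% |

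The last row arises because, with the unpooled statistic, 13/13 is significant only against 0/4 (against 1/4, p = 0.063). Maximum power is then (1 − p)⁴, which falls below 80% at p = 1 − 0.8^(1/4) = 5.4%.

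**The case against.** The plan already says that power is limited and that detectable differences are large, and it puts estimation first. Table 6-3 shows how wide the intervals are (2 of 4: 15 to 85%). Dose escalation rests on safety data, and Section 6.4.4.3 also plans comparison of response magnitudes. All of that stands: the plan does not claim adequate power, and neither the decision to escalate nor the whole dose evaluation hangs on this test.

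Four stronger readings are tempting and are not supported.

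- A reader might infer that the statement on detectable differences fails everywhere above 5%. It does not: at Group 1 rates of 10, 20 and 30%, both power targets remain attainable. It fails above about 32% (90% power) or 42% (80% power).
- A reader might infer that the table uses the wrong comparator. Section 6.1.2 introduces it as a comparison of the two vaccine arms, which is the planned one. Only the range of rates is too narrow.
- A reader might take the macaque results to mean that the 500 mcg response rate will be high. Those results concern MPER-656 antibodies at 1 mg, or titers with four animals per group. The planned endpoint is human positivity to the 2F5 epitope, whose rate is unknown.
- A reader might treat 42% as fixed. It depends on the evaluable numbers and the test statistic, as Step 4 shows.

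What the plan's caveat does not convey is that a limit exists at all. Low power for a given difference and no attainable power for any difference are different statements.

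**Conclusion.** The point holds as a gap in the stated power and a limit that is not disclosed. The only power table for the planned dose comparison covers 0 to 5% in an active-dose arm and omits the 10 to 90% that the same section considers elsewhere. At 4 vs 13 evaluable, no Group 2 rate gives 80% power above a Group 1 rate of about 42%, or 90% power above about 32%. This assumes a two-sided 0.05 level, exact Fisher or pooled Barnard, and Group 1 as the lower arm. Whether the trial falls in that region depends on a human response rate that the documents do not give.

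The correction works in both directions. Within 0 to 5%, exact calculation with the planned test is more favourable than the printed cells (69/74 against 89/97 at 0%). At higher Group 1 rates the picture is worse than the text implies.

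**What to change.** In Section 6.1.2, recompute Table 6-5 by exact enumeration with the planned Barnard test and name the statistic. Label Arm 1 as Group 1 (500 mcg, n = 4) and Arm 2 as Group 2 (2000 mcg, n = 13). Use Group 1 rates of 0, 5, 10, 20, 30, 40 and 50% or more. With the pooled statistic, the minimum Group 2 rates rounded up to whole percentages, for 80%/90% power, are 69/74, 75/83, 81/89, 90/96, 96/100, 100/not attainable, and not attainable for either.

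Add a sentence making three statements:

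- With 4 and 13 evaluable, 80% (90%) power cannot be reached for any increase if the Group 1 rate exceeds about 42% (32%).
- With 5 and 15 evaluable, the 80% limit is about 51% by pooled Barnard and 33% by Fisher.
- A non-significant test in that range does not indicate absence of a dose effect.

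The cost is one table and one sentence, with no added participants, samples or assays. The downside is a less favourable power statement at higher Group 1 rates.

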6.4.4 Immunogenicity analysis

6.4.4.1 General approach

For the statistical analysis of immunogenicity endpoints, data from enrolled participants will be used according to the initial randomization assignment regardless of how many injections they received. Additional analyses may be performed, limited to participants who received all scheduled injections per protocol. Assay results that are unreliable, from specimens collected outside of the visit window, or from HIV-infected participants postinfection are excluded. Since the exact date of HIV infection is unknown, any assay data from blood draws 4 weeks prior to an infected participant's last seronegative sample and thereafter may be excluded. If an HIV-infected participant does not have a seronegative sample postenrollment, then all data from that participant may be excluded from the analysis.

Discrete categorical assay endpoints (eg, response rates) will be analyzed by tabulating the frequency of positive response for each assay by antigen and treatment arm at each timepoint for which an assessment is performed. Crude response rates will be presented with their corresponding 95% confidence interval estimates calculated using the score test method (33). Because of the small numbers of control participants in each group, no adjustment will be made to the vaccine arm estimates for the false positive rates in the control arms. Barnard or Fisher's exact tests, as specified in the SAP, will be used to compare the response rates of any 2 vaccine arms, with a significant difference declared if the 2-sided p-value is ≤ 0.05 . In general Barnard's is preferred since under most circumstances it is more powerful than Fisher's (34).

In addition to response rate estimates for each timepoint, the probability of observing at least 1 positive response by a given timepoint and the probability of observing more than 1 positive response by a given timepoint will be estimated, with corresponding confidence intervals, for each vaccine arm using maximum likelihood-based methods (35).

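### Table 6-5 does not follow from the two-sided Fisher's exact test it cites: its detectable response rates are 12 to 31 points too high, and its arm sizes look reversed

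*Combined protocol and SAP*

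**What the plan says.** Section 6.1.2 gives the evaluable vaccine-arm sizes, after 10% missing data, as 4 for Group 1 and 13 for Group 2. Table 6-5 is titled "Power for comparison of response rates between 2 arms", with n1 = 13 and n2 = 4. Its left column is the true Arm 1 rate, from 0% to 5%. The other columns give the "Minimum true response rate in Arm 2 in order to detect a difference": 89, 90, 91, 92, 92, 93 for 80% power and 97, 97, 98, 99, 99, 100 for 90% power. The stated method is a Fisher's "exact 2-sided test with a Type I error rate of 0.05". No approximation is mentioned, and Arms 1 and 2 are not tied to Groups 1 and 2.

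For the Group 1 versus Group 2 analysis, the same section says it will "test superiority of the rate of responses targeting the 2F5 binding site by" Barnard's exact test. Section 6.4.4.1 is looser: Barnard or Fisher's "exact tests, as specified in the SAP, will be used to compare the response rates of any 2 vaccine arms", with Barnard generally preferred as more powerful.

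**The concern.** With arms this small, the power of an exact test can be worked out by hand, and the printed rates look much too high for the test named. Table 6-5 is the only power benchmark in the plan for comparing response rates between the two dose groups. If its entries do not come from the stated test, the reader is misled about what the comparison can detect and cannot reproduce the calculation. If the arm sizes are also reversed, the reader takes the wrong arm as the low-rate reference.

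**Working it through.** **Inputs (Section 6.1.2).** Arm sizes 13 and 4; two-sided alpha 0.05; power 80% and 90%; Arm 1 rates 0% to 5%; the 12 entries of Table 6-5; the Pr(2+/4) column of Table 6-4.

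**1. Reproducing the printed entries.** The stated test does not produce them (steps 2 to 4). Nor, with the arms as titled, does any variant tried: one-sided Fisher, smaller alpha, chi-square with or without correction, Barnard, Boschloo, normal approximations, other arm sizes. One calculation does, with Arm 1 = 4 and Arm 2 = 13: the continuity-corrected arcsine approximation,

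power = Φ( √[4·n1·n2/(n1+n2)] × { asin√(p2 − 1/(2·n2)) − asin√(p1 + 1/(2·n1)) } − 1.960 ).

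For 0% versus 89%: √(4·4·13/17) = 3.498; asin√(0.89 − 1/26) = 1.175; asin√(1/8) = 0.361; so Φ(3.498 × 0.814 − 1.960) = 0.812. At 88% it is 0.799, so 89 is the smallest whole percent that reaches 80%. At 5% versus 100% it gives 0.909, and at 99% it gives 0.894. Applied to the whole table:

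- n = 4 as Arm 1: 12 of 12 entries match.
- n = 13 as Arm 1, as titled: 3 of 12 match, and 90% power is not reached at Arm 1 rates of 4% and 5%.

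**2. Stated test, arms as titled, 0% row.** With 0/13 in Arm 1, Fisher gives p = 0.235 against 1/4 and p = 0.044 against 2/4. It therefore rejects exactly when Arm 2 has two or more responders, and power equals Pr(2+/4) = 1 − (1−p)⁴ − 4p(1−p)³.

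- p = 0.60: 1 − 0.0256 − 0.1536 = 0.821
- p = 0.70: 1 − 0.0081 − 0.0756 = 0.916

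Table 6-4 prints the same values, 82.1% and 91.6%. So 80% and 90% power are reached by 60% and 70%, where Table 6-5 says 89% and 97%.

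**3. Stated test, sizes swapped, 0% row.** With 0/4 in the low-rate arm, Fisher first rejects at 9/13 (p = 0.029). Power is Pr(9+/13), which reaches 80% at 75.2% and 90% at 80.0%.

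**4. All rows.** For each of the 14 × 5 = 70 outcomes, the two-sided Fisher p-value was computed. The two binomial probabilities were multiplied and summed over outcomes with p ≤ 0.05, and the result was solved for the rate giving 80% or 90% power. Each cell below shows the 80% / 90% rates.

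| Arm 1 rate | Table 6-5 | Exact Fisher, n = 13 low (as titled) | Exact Fisher, n = 4 low | Exact Barnard, n = 4 low |
|---|---|---|---|---|
| 0% | 89 / 97 | 58.2 / 68.0 | 75.2 / 80.0 | 68.4 / 73.6 |
| 1% | 90 / 97 | 62.0 / 72.3 | 76.4 / 81.6 | 69.5 / 75.3 |
| 2% | 91 / 98 | 65.8 / 76.4 | 77.5 / 83.3 | 70.7 / 77.0 |
| 3% | 92 / 99 | 69.4 / 80.1 | 78.8 / 85.1 | 72.0 / 78.7 |
| 4% | 92 / 99 | 72.8 / 83.3 | 80.1 / 86.8 | 73.3 / 80.4 |
| 5% | 93 / 100 | 76.0 / 86.1 | 81.4 / 88.3 | 74.6 / 82.0 |

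Before rounding, the excess of the printed over the exact Fisher rate is 13.9 to 30.8 points as titled and 11.6 to 17.1 points with n = 4 low. Over both orientations, exact Fisher power at the entries in the 80% column is 95.1% to 99.5%, and in the 90% column at least 99.6%.

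**5. The planned test.** Barnard's test (pooled z statistic, unconditional) rejects from 0/4 versus 8/13 (p = 0.042), one responder earlier than Fisher. For 0% in the arm of 4 and 80% in the arm of 13, exact power is 90.1% with Fisher and 97.0% with Barnard. Table 6-5 implies that 80% falls short of even 80% power.

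**The case against.** The strongest reply is that nothing turns on this table. Section 6.1.2 describes the immunogenicity aim as preliminary estimation of response rates and introduces Table 6-5 only to show that a formal comparison has little power. With correct values, the detectable contrast is still roughly 0% to 5% against 58% to 88%. The error is on the cautious side, and no arm size, analysis or decision rests on it. All of that stands and limits the weight of the point. It does not make the printed figures right for the test named.

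Second, the reversed labels and the arcsine method are reverse engineering. The plan never says that Arm 1 is Group 1, and the title order agrees with the sentence that introduces the table. That is fair: a match of 12 of 12 against 3 of 12 is strong evidence but not a statement in the plan. The main finding does not need it, because the entries fail in both orientations and Table 6-4 contradicts the 0% row as titled.

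Third, powering on Fisher while planning Barnard is a permissible, disclosed and conservative choice. That also stands; the difference between the two tests is not a separate error.

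**Conclusion.** The concern holds. No entry of Table 6-5 follows from a two-sided Fisher's exact test at 0.05 with 13 and 4 participants, whichever arm has the low rate. The excess is 13.9 to 30.8 percentage points on the plan's own labels, or 11.6 to 17.1 points in the orientation that the numbers fit. This rests only on the stated sizes, the stated alpha, independent binomial responses and rejection at p ≤ 0.05. The likely source, a continuity-corrected arcsine approximation with the arm of 4 first and the sizes reversed in the title, is an inference from the match. The practical effect is modest: the table understates what the comparison can detect, but the statement that detectable differences are fairly large remains true.

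**What to change.** Recompute Table 6-5 by exact enumeration for the test that will be used (Barnard's as Section 6.1.2 plans, or Fisher's if the SAP keeps it), and name that test in the sentence above the table. If an approximation is kept, name it and say that it is conservative at these sizes. State in the title and column headings which group is Arm 1 and which is Arm 2. If the low-rate reference is meant to be Group 1, that is Arm 1 = Group 1 (n = 4) and Arm 2 = Group 2 (n = 13). The sample size and the description of the detectable differences need no change. The cost is one recalculated table, its title and one sentence, with no operational effect.
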